14.1.4 Analysis of SRI-4 Response at Week 52 in Japanese versus non-Japanese Subjects

Following the review of the PA, the Japanese cohort will not be explored. All the listings produced for the PA will be updated to include the data of all Japanese subjects. Safety summaries of AEs and Labs will be presented for the Asia-Pacific subgroup (defined as sites in the trial from Korea, Taiwan, Japan, Philippines and Malaysia) vs non-Asia-Pacific subgroup.

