6.3 Analysis of Japanese Cohort

The plan was to perform two Japanese cohort analyses: 1) Partial Japanese cohort analysis at the time of primary analysis; and 2) Final Japanese cohort analysis at the time of final analysis. However, after review of PA results, the study was terminated. The data of the Japanese cohort will be included in data listings at the time of the LTE analysis when all subjects either completed or early terminated the study and the full database is locked.

The analysis of the partial Japanese cohort was performed with the Japanese subjects available in the database of primary analysis cohort who:

- Completed Week 52 of treatment and either entered LTE or completed Safety Follow-Up, or

- Prematurely discontinued from treatment prior to Week 52 and completed Safety Follow-Up, or
- Prematurely discontinued from study without Safety Follow-Up.

Data collected during the 52 weeks treatment period as well as during the corresponding safety follow-up visit was included in this analysis. Details were provided in the Interim Database Lock Plan for Analysis of Japanese Cohort.

Certain steps were taken to ensure protection of the blind of the Japanese cohort subjects who would be followed-up in a double-blind manner after the PA. Details can be found in the Unblinding Plan.

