- The protocol specifies that flare-free status will be analyzed separately depending on severity, but in this IAP flare-free status is defined as not having any flares (defined with BILAG 2004 and SFI, separately) during the 52-week treatment period.
- The protocol mentions several endpoints for the analysis of corticosteroid usage over time. The first endpoint (i.e., reduction from baseline in prednisone-equivalent CS dose by $\geq 25\%$ to a dose of ≤ 7.5 mg/day, with no BILAG A or 2B flare in disease activity at that visit) is removed from this IAP. Analysis of the clinically meaningful reduction in CS dose from Baseline (defined as a reduction of daily prednisone-equivalent CS dose $\geq 25\%$ to a dose of ≤ 7.5 mg/day by Week 40 and sustained through Week 52 AND no new BILAG A organ domain scores and no more than one new BILAG B organ domain score during Weeks 40 through 52) will be sufficient.
- SRI definition specified in the protocol includes ‘no discontinuation of investigational product’, but this condition has been removed from this IAP (see Section 14.1.1). Subjects with missing response at Week 52 have been added as a condition of non-SRI responder, meaning that all subjects who prematurely discontinued treatment will be considered as non-SRI responder.
- For definition of SRI responses, LDA Definition #2, LLDAS and BICLA, EAC-treatment failure assessment will be used to consider subjects as non-responder in these 3 endpoints.
- Due to study termination, the analysis of Japanese cohort and LTE analysis will be performed simultaneously. The Japanese cohort will not be explored for consistency, the listings produced for the PA will be rerun including all Japanese subjects. A safety summary of Asia-Pacific subjects will be presented during the 52-Week treatment period (see Section 14.1.4). The LTE analysis will be reduced with a focus on safety, further details can be found in Sections 14.6 and 15.

8 Protocol Deviations and Analysis Sets

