8.2.2 Analysis Sets

Table 3 provides the definitions of the Analysis Sets and their purposes.

[figure not shown]
The analysis sets for PA will be drawn from all subjects randomized as of November 28, 2018 (n = 469), see Sections 6.2 and 7. Subjects not randomized (screen failure) will be included in PA analysis set if their screening date is on or before November 28, 2018. For the LTE analysis, the analysis sets will be drawn from all subjects who enter the LTE.

For analysis on HDA subpopulation, all subjects with SLEDAI-2K ≥ 10 at Screening will be included. The corresponding analysis sets will be drawn as specified above depending on the analysis (PA, LTE analysis).

Table 3: Analysis Sets

Analysis Set	Definition	Purpose
Enrolled	The Enrolled analysis set will include all subjects who sign the informed consent form.	The purpose of this analysis set is to count how many subjects signed the informed consent

ITT (Intent-To-Treat) Analysis Set	The ITT analysis set will include all randomized subjects. Subjects will be analyzed according to randomization treatment.	The ITT will be used for demographic/baseline characteristics.
mITT (modified Intent-To-Treat) Analysis Set	The mITT analysis set will include all randomized subjects who have received at least one dose of IMP (evobrutinib or placebo) and have at least one Baseline and one post-Baseline disease assessment (among the following: SFI, SLEDAI-2K, PGA, BILAG 2004, CLASI). Subjects will be analyzed according to randomized treatment. Subjects with Protocol Deviation (PD) code equal to PDEV80 are excluded from mITT.	The mITT will be used for all efficacy endpoints. The mITT will be used for demographic/baseline characteristics in case more than 10% of ITT are excluded from mITT.
Safety Analysis Set (SAF)	The Safety analysis set will include all subjects who have received at least one dose of IMP (evobrutinib or placebo). Subjects will be analyzed according to the actual treatment they receive.	The SAF will be used for the analysis of medications, exposure/compliance and safety endpoints.

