Time to first flare, flare-free status and annualized flare rate	
Time to first flare, flare-free status and annualized flare rate will be analyzed as in Section 14.3.2 at Week 24, Week 52 and Week 104 with descriptive statistics only. No statistical modeling will be performed.
 
Time to first flare will be assessed starting from randomization (Day 1 of 52-week treatment period) and will be derived for the whole treatment period.
 
Flare analyses will be censored at the time of announcements to the sites of study early termination (i.e. 23 March 2020)

15 Safety Evaluation

For all safety endpoints, data selection for PA and LTE analysis will be handled as indicated in the [Table 26](#).

Table 26 : Data Handling for Safety Analysis

Data summarized	Analysis	Analysis sets	Period covered	Treatment groups

 • AEs • Laboratory data • Vital signs • ECGs • Other safety evaluations 	PA	SAF	All data from 52-week treatment period (safety follow-up included)	
 • Placebo • Evobrutinib 25 mg QD • Evobrutinib 75 mg QD • Evobrutinib 50 mg BID
	LTE analysis	LTE SAF	All data from LTE period (safety follow-up posterior to LTE included)	
 • Placebo/Evobrutinib 50 mg BID • Evobrutinib 25 mg QD/Evobrutinib 50 mg BID • Evobrutinib 75 mg QD/Evobrutinib 50 mg BID • Evobrutinib 50 mg BID/Evobrutinib 50 mg BID

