15.1 Adverse Events

All analyses described in this section will be based on treatment-emergent adverse events (TEAEs) if not otherwise specified.

For the PA, TEAEs will be defined as:

- AEs starting on or after first treatment administration of any IMP (placebo or evobrutinib) until safety follow up (end of study) or first administration in LTE for subjects continuing in LTE,
- or if it was present prior to any IMP administration but exacerbated after.

Any AE which started before study first treatment administration of any IMP (placebo or evobrutinib) but improved during treatment period until safety follow up (end of study) or first administration in LTE for subjects continuing in LTE will not be counted as TEAE.

For the LTE analysis:

- For subjects who enter the LTE, TEAEs will be defined as:
 - AEs starting on or after first treatment administration of evobrutinib 50 mg BID during LTE until the end of study.
 - AEs starting prior first treatment administration of evobrutinib 50 mg BID during LTE, but exacerbated during the LTE

Only AEs from LTE period will be considered including AEs during the LTE safety follow-up period. Any AE which started before study first treatment administration of evobrutinib 50 mg BID but improved during LTE period will not be counted as TEAE.

Incomplete AE-related dates will be handled as follows:

- In case the onset date is missing completely or missing partially but the onset month and year, or the onset year are equal to the start of IMP then the onset date will be replaced by the minimum of start of IMP and AE resolution date.
- In all other cases the missing onset day or missing onset month will be replaced by 1.
- Incomplete stop dates will be replaced by the last day of the month (if day is missing only), if not resulting in a date later than the date of subject's death. In the latter case, the date of death will be used to impute the incomplete stop date.

Further information collected after the cut-off for an analysis (such as a fatal outcome) may be extracted from the Safety data base and presented separately in the CSR.

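### Double-blind safety events of subjects randomised after 28 November 2018 fall outside the main all-subject evobrutinib-versus-placebo 52-week safety tables

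*SAP*

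**What the plan says.** Section 8.2.2 ties the PA sets to a date: "The analysis sets for PA will be drawn from all subjects randomized as of November 28, 2018 (n = 469". The safety analysis set in Table 3 has no date limit of its own, so the restriction comes from this sentence and from Section 6.2. For the extension, the same section says: "For the LTE analysis, the analysis sets will be drawn from all subjects who enter the LTE".

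Table 26 in Section 15 then fixes the data period. The PA row covers "All data from 52-week treatment period (safety follow-up included"; the LTE row covers "All data from LTE period (safety follow-up posterior to LTE included". Section 15.1 repeats the limit for the LTE analysis: "Only AEs from LTE period will be considered including AEs during the LTE safety follow-up period".

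Section 6.3 shows that the PA cohort is not the whole trial. It describes "protection of the blind of the Japanese cohort subjects who would be followed-up in a double-blind manner after the PA". It also records that a final Japanese cohort analysis had been planned and that, after termination, the Japanese data go into listings at the time of the LTE analysis. Section 7 adds: "A safety summary of Asia-Pacific subjects will be presented during the 52-Week treatment period". Section 14.1.4 describes the same two replacements. On the listings it says: "All the listings produced for the PA will be updated to include the data of all Japanese subjects". It then plans regional summaries of adverse events and laboratory data, and gives the countries that make up the Asia-Pacific subgroup.

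**The concern.** Safety is part of the primary objective in Table 1. The LTE analysis takes place on the full locked database, and the SAP describes no later analysis. A serious event, death or liver event during randomised, placebo-controlled treatment in a late subject would be left out of the main evobrutinib-versus-placebo rates, although it is in the same database. The late subjects that the SAP implies all come from one region, so the omission is not spread evenly over the trial population.

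**Working it through.** **Tracing a subject randomised after the cut-off**

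1. PA safety tables: excluded by randomisation date (Sections 6.2 and 8.2.2).
2. LTE safety tables, subject never enters the LTE: excluded, because the LTE sets contain entrants only (Section 8.2.2).
3. LTE safety tables, subject enters the LTE: included, but only with LTE-period data (Table 26, Section 15.1). The double-blind events are still not counted.
4. Other planned tables: Table 29 has columns for the PA, the LTE analysis and the high-disease-activity subpopulation of the PA. The three-tier adverse event comparison with placebo, which includes the Tier 1 transaminase terms, is for the PA only (Section 15.1.1.1). No section plans a re-run of the by-arm 52-week safety tables on all treated subjects.
5. Re-run PA listings: included if Japanese (Sections 6.3, 7 and 14.1.4).
6. Asia-Pacific versus non-Asia-Pacific summaries: included on the natural reading, for adverse events and laboratory data over 52 weeks. Section 14.1.4 names no analysis set and does not say whether serious events, deaths and adverse events of special interest are shown.
7. Double-blind vital signs, ECG, immunoglobulins, B cells and C-SSRS: listed only. They have their own subsections (15.4, 15.5, 15.8, 15.9 and 15.11), and the regional summary does not mention them.

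**Size**

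Inputs: 469 randomised in the PA cohort (Section 8.2.2); 36 Japanese subjects planned, out of 432 (Section 8.2.1); allocation 1:1:1:1. The plan's own share reproduces: 36/432 = 8.3%.

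The number *k* randomised late is not given. Assume that late subjects are all Japanese and that the cohort did not exceed 36. Sections 6.3 and 14.1.3 (the Partial Japan label) show that some Japanese subjects are already in the PA, so *k* is at most 35.

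- Share outside the main tables = *k*/(469 + *k*).
- *k* = 1: 1/470 = 0.2%.
- *k* = 12: 12/481 = 2.5%.
- *k* = 35: 35/504 = 6.9%, and 35/4 = 8.75, so fewer than 9 per arm on average.

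The denominator is randomised subjects; the number dosed is not stated.

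The chance that at least one affected subject is left out is 1 − (1 − *p*)^*k*, where *p* is an assumed one-year event risk that the SAP does not supply:

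- *p* = 5%: 1 − 0.95^12 = 46%; 1 − 0.95^35 = 83%.
- *p* = 1%: 1 − 0.99^12 = 11%; 1 − 0.99^35 = 30%.

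**The case against.** A reader might infer that these subjects' deaths, serious events and liver events go unreported, or appear in no by-arm summary. The documents do not support that.

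- The re-run listings cover deaths, serious events, flagged events of special interest, and the high-grade laboratory values in Section 15.3.
- The two regional columns together partition all subjects. Section 9.2 orders tables by treatment group as a general rule, so by-arm presentation of the regional summary is the default. A fatal or serious treatment-emergent event would ordinarily belong in a summary of adverse events.
- Section 15.1 allows information that arrives after a cut-off, such as a fatal outcome, to be presented separately in the CSR. This is permissive and outside the rate tables.
- Some LTE outputs reach back. Section 13.1 summarises exposure over the whole study for LTE entrants on 50 mg BID throughout, and the LTE time-to-event figures for ALT and eGFR in Section 15.3 start at the 52-week baseline. Neither helps a late subject who never enters the LTE.

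A reader might also take all 36 planned Japanese subjects as missing. That cannot be so, because some are in the PA, and 36 is a planned number, not a recruited one.

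Keeping late subjects apart is also defensible. They were still under double-blind follow-up when the study was terminated, COVID-19 caused disruption (Section 15.16), and Section 7 discloses the change. Their exposure may be shorter and their data less complete than the PA cohort's. That supports a footnote and exposure-adjusted rates, but it does not justify having no all-subject comparison.

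What stands against the objection is narrow: a regional split with no stated analysis set is not the all-subject controlled comparison, and nothing else in the plan supplies it.

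**Conclusion.** The point holds as a gap in completeness, not as a loss of data. Double-blind events in subjects randomised after 28 November 2018 are absent from the main by-arm 52-week safety tables, whether or not the subject later enters the LTE. They appear in re-run listings and, on the natural reading, in the Asia-Pacific summaries of adverse events and laboratory data.

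The share affected is unknown and lies between 0.2% and 6.9% if the late subjects are only Japanese and no more than 36 were recruited. Any late non-Japanese subject would add to it and would not clearly be covered even by the re-run listings; the SAP neither states nor excludes such subjects. The effect on overall rates is likely to be small. For rare serious events, however, one omitted case can change a by-arm count, and safety is a primary objective, so the change is worth making. No PA efficacy result is affected.

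**What to change.** - In Section 8.2.2 and Table 26, define a final 52-week safety set of all randomised and dosed subjects, whatever their randomisation date, and state how many were randomised after the cut-off.
- At final lock, re-run the core by-arm tables on that set: exposure, treatment-emergent adverse events, serious events, deaths, events of special interest, exposure-adjusted incidence rates and liver laboratory shifts. Re-running every safety output is more than the gap requires.
- In Section 14.1.4, name the same set for the Asia-Pacific summary, state its serious-event, death and special-interest content, and add an all-subject column by arm.
- Footnote the difference from the PA counts.

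The cost is SAP wording and a re-run of existing table programs. The downside is a second set of 52-week safety counts that differs slightly from the PA set and has to be reconciled in the CSR. The PA efficacy cohort and the testing procedure stay as they are.

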14.2 Key secondary endpoints

The key secondary endpoints will be analyzed for the PA on the mITT analysis set.

The key secondary endpoints are the following:

- SRI-4 response at Week 52 among serologically active subgroup.
- Time to first severe (BILAG A) flare

14.2.1 Definitions

SRI-4 response among serologically active subjects

The SRI-4 response will be analyzed at Week 52 among subjects who are serologically active at screening, i.e., positive anti-dsDNA or low complement levels.

Time to first severe (BILAG A) flare

A severe (BILAG A) flare is defined as at least one BILAG A score in any organ system due to items that are new or worse, compared to the BILAG evaluation at the previous visit, during the 52-week treatment period. “Due to items that were new or worse” means that if the assigned Grade A/B or C contains ANY ITEM which is WORSE or NEW, such grade will be included into the flare consideration. This is valid for clinical organ domains. For laboratory organ domains (i.e. renal and hematological) where items are not worse/new, there has to be an increase in score from B to A or C to B for flare to be considered. Appendix 18.1.1 provides further details on BILAG evaluation. EAC will review the dry-run BILAG analysis dataset to ensure appropriateness and correctness of programmed BILAG flare derivation. Further details can be found in the EAC Charter.

Since subjects are only to be assessed for BILAG flare at discrete planned visits, the corresponding date of visit will be used to derive the time to first severe (BILAG A) flare as follows:

$$\begin{aligned} & \textit{Time to first severe BILAG A flare (days)} \\ &= \textit{Date of visit where the first severe BILAG A flare has been diagnosed} \\ & - \textit{Date of randomization} + 1 \end{aligned}$$

The following censoring rules will be used:

- A subject discontinuing the 52-week treatment period prior to Week 52 without severe flare will have his/her time to first severe flare right-censored at the last time point at which flare could be assessed (i.e. treatment discontinuation date).
- A subject completing the 52-week treatment period without severe flare will have his/her time to first severe flare right-censored at Week 52.

Additionally, a sensitivity analysis will be performed based on Multiple imputation approach of severe flare at each visit up to week 52:

- Monotone missing data structure will be created as follows: intermediate (non-monotone) missing data will be multiply imputed using the Markov chain Monte Carlo (MCMC) method and assuming MAR and multivariate log normality. The SAS procedure PROC MI with the MCMC option will be used with seed number = 2005270018. The number of burn-in iterations will be set to 200, which is the default value. Nevertheless, if diagnosis plots show that the convergence has not yet occurred, this will be adjusted.
- Then the response (Severe BILAG A: Yes/No) will be imputed with treatment group, race, region, SLEDAI-2K total score (<10; >=10) and response at previous visit covariates.
- Imputation will be repeated 1000 times. Then depending of the visit of censored observation or of response, the time to first severe BILAG A flare will be computed as described for the non- sensitivity analysis. Estimate and associated standard error of Cox regression analysis applied on each imputed sample will be combined using MIANALYZE SAS procedure with the Rubin’s rules as described in Appendix 18.9.

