For efficacy and safety analyses, each measurement will be assigned an analysis visit number first according to the prespecified time window. The analysis visit will then be used for missing data imputations, analysis variable derivations, statistical calculations and presentations. Safety follow-up will not be included in analysis visit calculations, only assessments collected under treatment visits and no more than 14 days after last exposure date will be used.

For by visit summary of safety endpoints (e.g. laboratory and vital sign assessments), data collected during the safety follow-up will be shown, presenting separately data from subjects who completed safety follow-up and who discontinued during safety follow-up.

For subject data listings by time point, the nominal visit (as collected in the database) as well as the analysis visit will be displayed.

For the calculation of analysis visit using the time windows, 1 month is expressed as 30 days.

[figure not shown]
As the schedule of assessments is different for each visit, specific time windows must be used for each endpoint. They are defined in Appendix 18.11.

If there are multiple assessments within a same visit window, then the one closest to the target day will be used. If two assessments have the same difference with target day, the earlier one will be used.

Unblinding:

Details regarding the unblinding process are available in the Unblinding Plan.

CCI

10 Trial Subjects

The subsections in this section include specifications for reporting subject disposition and treatment/trial discontinuations. Additionally, procedures for reporting protocol deviations are provided.

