The compliance will be computed using the number of kits dispensed as well as the number of tablets returned. Compliance with treatment will be tabulated by treatment group from first intake in LTE to last intake during LTE period and also presented within categories, as for the 52-week treatment period.

The first kit dispensed in LTE treatment period is at Week 52 visit for subjects who rolled over directly from 52-week treatment to LTE.

LTE analysis: Overall period (i.e. 52-week treatment period + LTE)

Overall compliance will be presented on LTE SAF only on subjects who received evobrutinib 50 mg BID during the 52-week treatment period and continue with the same dose of evobrutinib during LTE period.

Overall compliance with treatment is defined using the formula below:

$$\text{Compliance with treatment} = 100 \times \left[\left(\frac{N_1}{5 \times N_2} \right) + \left(\frac{N_3}{4 \times N_4} \right) \right] / 2$$

where

- N_1 = number of tablets given minus number of tablets returned over N_2 days for the 52-week treatment period
- N_2 = number of days between treatment start and treatment termination visit for the 52-week treatment period
- N_3 = number of tablets given minus number of tablets returned over N_2 days for the LTE treatment period
- N_4 = number of days between treatment start and treatment termination visit for the LTE treatment period

Compliance with treatment will be tabulated from first intake to last intake of the study and also presented within categories, as for the 52-week treatment period.

Subject data listings:

For each analysis, the following listings will be provided:

- listing of kit numbers with date of dispense, and number of tablets returned (from BATCH).
- listing of start/end dates with number ingested tablets (from EXPOSUREDT).
- listing with exposure time, cumulative dose, and compliance.

14 Endpoint Evaluation

For all efficacy endpoints:

- Analysis visits will be used (as detailed in Section 9.7 and Appendix 18.11).
- Baseline definition from Section 9.5 should be applied.
- Statistical tests of the two-primary and key secondary efficacy endpoints entering the hierarchical testing procedure (see section 14.1.2.4) will be conducted at a one-sided α level of 0.025. The one-sided p-values and the two-sided 95% CIs will be presented as well as a note on how to interpret correctly the two-sided 95% CIs by considering appropriately the accurate boundary of the interval.

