18.11 Time Windows

Table 51: Time Windows for SFI, SLEDAI-2K, PGA, BILAG 2004

Analysis	Treatment groups	Period covered	Interval (days) [Date of assessment – Date of first dose + 1]	Analysis Visit

 PA Japanese cohort analysis 	
 Placebo Evobrutinib 25 mg QD Evobrutinib 75 mg QD Evobrutinib 50 mg BID 	52-week treatment period	1	Day 1
			[2 ; 42)	Week 4 – Day 29
			[42 ; 70)	Week 8 – Day 57
			[70 ; 98)	Week 12 – Day 85
			[98 ; 126)	Week 16 – Day 113
			[126 ; 154)	Week 20 – Day 141
			[154 ; 182)	Week 24 – Day 169
			[182 ; 210)	Week 28 – Day 197
			[210 ; 238)	Week 32 – Day 225
			[238 ; 266)	Week 36 – Day 253
			[266 ; 294)	Week 40 – Day 281
			[294 ; 322)	Week 44 – Day 309
			[322 ; 350)	Week 48 – Day 337
≥ 350*	Week 52 – Day 365			

 LTE analysis 	
 Placebo/Evobrutinib 50 mg BID Evobrutinib 25 mg QD/Evobrutinib 50 mg BID Evobrutinib 75 mg QD/Evobrutinib 50 mg BID Evobrutinib 50 mg BID/Evobrutinib 50 mg BID 	52-week treatment period	NA	NA
		LTE period	1	Day 1 – LTE
			[2 ; 266)	Week 24 - Day 169 – LTE
			[266 ; 554)	Week 52 - Day 365 – LTE
			[554 ; 751)	Week 104 - Day 745 – LTE

* Assessments performed more than 14 days after last exposure date will not be included as well as assessments collected during safety follow-up visit.

Table 52: Time Windows for CLASI

Analysis	Treatment groups	Period covered	Interval (days) [Date of assessment – Date of first dose + 1]	Analysis Visit
• PA	
 • Placebo • Evobrutinib 25 mg QD • Evobrutinib 75 mg QD • Evobrutinib 50 mg BID 	52-week treatment period	1	Day 1
			[2 ; 21)	Week 2 – Day 15
			[21 ; 42)	Week 4 – Day 29
			[42 ; 70)	Week 8 – Day 57
			[70 ; 98)	Week 12 – Day 85
			[98 ; 126)	Week 16 – Day 113
			[126 ; 154)	Week 20 – Day 141
			[154 ; 182)	Week 24 – Day 169
			[182 ; 210)	Week 28 – Day 197
			[210 ; 238)	Week 32 – Day 225
			[238 ; 266)	Week 36 – Day 253
			[266 ; 294)	Week 40 – Day 281
			[294 ; 322)	Week 44 – Day 309
[322 ; 350)	Week 48 – Day 337			
	≥ 350*	Week 52 – Day 365		
• LTE analysis	
 • Placebo/Evobrutinib 50 mg BID • Evobrutinib 25 mg QD/Evobrutinib 50 mg BID • Evobrutinib 75 mg QD/Evobrutinib 50 mg BID • Evobrutinib 50 mg BID/Evobrutinib 50 mg BID 	52-week treatment period	NA	NA
		LTE period	1	Day 1 – LTE
			[2 ; 266)	Week 24 - Day 169 – LTE
			[266 ; 554)	Week 52 - Day 365 – LTE

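### Flare-free discontinuers are censored at the treatment discontinuation date although BILAG flares are dated at visits accepted up to 14 days after last exposure, and the Week 52 censoring date for completers is not defined

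*SAP*

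**What the plan says.** Time to first severe BILAG A flare is a key secondary endpoint and step 3 of the testing order in Section 14.1.2.4.

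- **Events** (Section 14.2.1): "the corresponding date of visit will be used to derive the time to first severe (BILAG A) flare", counted from randomization.
- **Discontinuers without flare** (same section): time is "right-censored at the last time point at which flare could be assessed (i.e. treatment discontinuation date").
- **Completers without flare**: "A subject completing the 52-week treatment period without severe flare will have his/her time to first severe flare right-censored at Week 52". No calendar or study-day meaning is attached to Week 52.
- **Usable assessments**: the introduction to Section 14 states for all efficacy endpoints that "Analysis visits will be used (as detailed in Section 9.7 and Appendix 18.11"). Section 9.7 then says that "only assessments collected under treatment visits and no more than 14 days after last exposure date will be used". The footnote to Table 51, which covers BILAG, repeats the limit: "Assessments performed more than 14 days after last exposure date will not be included as well as assessments collected during safety follow-up visit". Table 51 gives Week 52 a target of Day 365 and a window from Day 350 with no upper day.

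Table 20 sends the moderate-to-severe BILAG flare and severe SFI flare analyses to the same censoring rules.

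**The concern.** For an outcome seen only at visits, event and censoring times should come from the same clock. Here an event carries a visit date and a discontinuer's censoring time carries a treatment date. The SAP treats the treatment date as the last moment at which flare could be assessed, yet its own window rules admit later assessments. Length of follow-up can then depend on what the final visit shows.

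The mismatch also runs the other way. If a subject stops between visits and has no final visit, the time from the last BILAG assessment to the stop date is counted as flare-free. Section 18.1.1.9 sets BILAG flare to missing, not absent, when a visit is wholly missed.

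The open meaning of Week 52 adds a smaller ambiguity. Two programmers could derive different times for the same completer, and one of the derivations damages the end of the Kaplan-Meier curve. Section 14.2.2.2 asks for that curve, with the median, its confidence interval, Q1, Q3 and the 5% to 20% percentiles.

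**Working it through.** The SAP gives no event count, hazard ratio or power for this endpoint, so there is no figure of its own to reproduce.

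**1. Discontinuers.** Let S be the stop date and k the days from S to the final treatment visit, with k between 0 and 14 (Section 9.7, Table 51).

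- Flare found at that visit: event at S + k.
- No flare at that visit: censored at S.
- Difference: (S + k) − S = k, so up to 14 days.
- No final visit: adjacent targets in Table 51 are 28 days apart (for example 141 − 113 = 28). Up to about 28 unassessed days count as flare-free, more after missed visits.

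Scale, assuming 108 per arm (Section 8.2.1) and 20% discontinuation (assumed): 0.20 × 108 = 21.6 subjects. Lost time is at most 21.6 × 14 = 302 days. Credited time, with no missed visits, is at most 21.6 × 28 = 605 days. Against 108 × 365 = 39,420 nominal person-days these are 0.8% and 1.5%.

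**2. Completers.** If Week 52 is the visit date, events and censoring share one clock. If it is Day 365, a flare found at a Week 52 visit on Day 370 falls after all flare-free completers have been censored. If that subject is the only one left, the Kaplan-Meier factor is 1 − 1/1 = 0 and the curve ends at 0.

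**3. Simulated effect on test and curve.** There were two arms of 108, and both rules were applied to the same simulated data. Rule A censors discontinuers at stop and completers at Day 365, the less favourable reading. Rule B censors at the last BILAG assessment. None of the following is in the SAP: placebo one-year flare risk 10%, 20% or 30%; HR 0.5 or 1; 20% discontinuation (or 10% placebo, 30% active); a final visit 0 to 14 days after stop for every discontinuer; visits every 28 days ± 7 days. The test was an unstratified log-rank at one-sided 0.025, with 600 trials per scenario (1,200 under HR 1). Cells show A → B.

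| Scenario | Events after last censoring, per trial | Placebo curve ends at 0 | Peto HR | Rejections |
|---|---|---|---|---|
| 10%, HR 0.5 | 0.50 → 0.00 | 29% → 0% | 0.525 → 0.524 | 20.7% → 21.7% |
| 20%, HR 0.5 | 0.92 → 0.00 | 48% → 0% | 0.516 → 0.513 | 41.8% → 42.5% |
| 30%, HR 0.5 | 1.34 → 0.01 | 57% → 1% | 0.519 → 0.517 | 59.7% → 61.2% |
| 20%, HR 1 | 1.23 → 0.00 | 47% → 0% | 0.993 → 0.992 | 2.2% → 2.2% |
| 20%, HR 1, 10% vs 30% discontinuing | 1.21 → 0.00 | 50% → 0% | 1.012 → 1.008 | 2.0% → 1.8% |
| 20%, HR 0.5, visits exactly on target | 0.01 → 0.01 | 1% → 1% | 0.499 → 0.499 | 45.5% → 45.5% |

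Power differences with ± 7 days are 1.0, 0.7 and 1.5 points. The largest HR change is 1.012 − 1.008 = 0.004. Monte Carlo standard error is about √(0.418 × 0.582 / 600) = 2.0 points for power and √(0.022 × 0.978 / 1200) = 0.4 points under the null. The A–B differences are less noisy because the data are shared.

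**4. Which reading causes the collapse.** A one-arm simulation (110 subjects, 20% risk, 20% drop-out, 70% of drop-outs with a final visit 0 to 14 days after stop, visits −3 to +7 days, 200 arms; all but the 14-day limit assumed) gave a mean final Kaplan-Meier estimate of 0.353 under Day 365, with 0 reached in 56.5% of arms, against 0.773 under last-assessment censoring. With completers censored at the visit date it was 0.768 under both rules.

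**The case against.** The discontinuer rule states the right principle and only its parenthesis is loose. The recorded discontinuation date might be that of the termination visit; Section 13.2 counts days to a treatment termination visit and equates them with exposure time. The 14-day limit bounds usable data and does not show that such gaps occur. For completers, the SAP's usage points to the visit: analysis visits govern efficacy endpoints, Section 18.8.1.4 uses a subject-specific Week 52 date, the multiple-imputation text in Section 14.2.1 ties censoring to a visit, and Section 15.3 names a fixed day (398) where one is wanted. The multiple-imputation analysis also imputes flare status by visit to Week 52, so it does not simply credit time after drop-out.

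Most of this stands. It makes the Day 365 reading the less natural one, and the discontinuer problem conditional on what the discontinuation date is. It does not settle the wording. Section 13.1, to which Section 13.2 refers for exposure time, uses the last-dose date, and Section 18.8.1.4 counts visits up to 14 days after last intake as within the treatment period.

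A reader might infer three stronger points that the documents do not support:

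- That the plan's rule makes the curve collapse. This needs Day 365 and visits off target.
- That the confirmatory test is compromised, or that credited time understates the hazard in the arm with more drop-outs. The simulations show no visible type I error inflation, and no figure supports a hazard bias.
- That SFI flares share the visit-dating mechanism. Section 14.3.2.1 dates severe SFI flares from the SFI2 form, so only the censoring rule carries over.

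**Conclusion.** The inconsistency is real but modest. If the discontinuation date is the stop or last-dose date, a BILAG event can fall up to 14 days after the censoring time of a flare-free subject seen at the same visit, and unassessed time before stopping can be counted as flare-free. The Week 52 date for completers needs defining, although the visit date is its natural meaning.

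In the assumed scenarios the log-rank test and HR are little affected, even under the less favourable Day 365 reading. What is exposed is mainly the Kaplan-Meier curve and its late percentiles, and on the visit-date reading the final estimate did not change either. Two limits apply. The two-arm runs gave every discontinuer a final visit, so the credited-time effect on the test is bounded only by the person-time arithmetic above. The collapse rate also depends heavily on assumed visit scatter: about 1% with none and 48% with ± 7 days at 20% risk.

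**What to change.** Replace both censoring bullets in Section 14.2.1 with one rule:

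- A subject without BILAG flare is censored at the date of the last evaluable on-treatment BILAG flare assessment, up to 14 days after last dose.
- For completers this is the actual Week 52 visit date.
- A subject with no post-baseline flare assessment is censored at Day 1.
- For SFI flares, censor at the last SFI assessment.

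The cost is SAP wording and one derivation line, plus slightly less follow-up time for drop-outs without a final visit. Section 6.4 shows that the primary analysis has already been reviewed, so any re-run of it under this rule should be labelled post hoc. The clinical study report should state which dates the reported analysis used for discontinuers and for completers.
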